- h Separate Hb should be collected at all the visits where Complete Blood Count (CBC) is not collected; i.e. Hb at weeks 5, 6, 7, 10 until the end of the study. It is recommended that the Hb assessments be performed on the same day of the patient's dialysis schedule throughout the study.
- i If during an unscheduled visit hemoglobin needs to be assessed, this should always be done with the HemoCue AND a central laboratory hemoglobin assessment.
- j Serum chemistry includes LFTs.
- k Renal ultrasound examination can be performed at any time during the screening period. Not required if results of a previous renal ultrasound (or other renal imaging modality such as CT scan or MRI providing a conclusive report on the kidney) within 12 weeks prior to randomization is available and ruling out renal cell carcinoma.

Footnotes continued on next page

- l LFTs to be collected at further visits where serum chemistry is not collected.
- m Fasting, whenever possible.
- n TSAT = [FeSat (Ferro Saturation = % Iron Saturation) measured by central lab and derived from iron and TIBC].
- o Human chorionic gonadotropin (HCG); to be collected from female subjects of childbearing potential only.
- p Only for subjects randomized to roxadustat at 6 time points over 1 to 3 visits. At each PK visit, an additional sample will be collected for albumin and alpha-acidglycoprotein determination.
- q Includes Short Form 36 (SF-36), Functional Assessment of Cancer Therapy-Anemia (FACT-An), European Quality of Life 5 Domain 5 Level (EQ-5D 5L) and Patients' Global Impression of Change (PGIC). PGIC will not be performed on day 1. In HD subjects, the quality of life questionnaires are to be completed by the subject prior to any other assessment or at the latest at the start of dialysis session. It is important that the physician does not discuss the status of the subject prior to completion of the questionnaires. In PD subjects the questionnaires are to be completed prior to any study assessment.
- r Only for continuous ambulatory peritoneal dialysis (CAPD) subjects randomized to roxadustat. Sample to be withdrawn from the drainage bag after draining complete volume at the site and at the same visit as the PK blood samples (see footnote o).

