6.1.1.2 Primary Efficacy Endpoint for US (FDA)

The primary efficacy endpoint for US is Hb change from BL to the average Hb of weeks 28 to 52 regardless of rescue therapy.

For the average in weeks 28-52, all available Hb values obtained from the central laboratory will be used (i.e., both scheduled and unscheduled Hb values).

For the analyses that require an Hb value by visit, the last available Hb value in the visit window will be kept.

In case a subject does not have any available Hb value during this week 28-52 period (because they died or withdrew from the study for example), imputation rules will be applied (refer to Section 7.11.1 for imputation rules).

Baseline Hb is defined as in Section 6.1.1.1

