6.1.2 Key Secondary Efficacy Endpoints

The key secondary efficacy endpoints in this study are listed in Table 5

Table 5 Key Secondary Efficacy Endpoints

Number	Endpoint
1	Hb response defined as mean Hb during weeks 28 to 36 within the target range of 10.0 to 12.0 g/dL without having received rescue therapy within 6 weeks prior to and during this 8-week evaluation period.
2	Change from BL in Low Density Lipoprotein (LDL) cholesterol to the average LDL cholesterol of weeks 12 to 28.
3	Mean monthly IV iron use (mg) during day 1 to week 36 (monthly defined as a period of 4 weeks).
4	Change from BL in SF-36 Physical Functioning (PF) sub-score to the average PF sub-score of weeks 12 to 28.
5	Change from BL in SF-36 Vitality (VT) sub-score to the average VT sub-score of weeks 12 to 28.
6	Change from BL in mean arterial pressure (MAP) to the average MAP value of weeks 20 to 28.
7	Time to first occurrence of increase in blood pressure: An increase from BL of ≥ 20 mm Hg systolic blood pressure (SBP) and SBP ≥ 170 mmHg or an increase from baseline of ≥ 15 mmHg diastolic blood pressure (DBP) and DBP ≥ 100 mmHg during weeks 1 to 36.

6.1.2.1 Hb response defined as mean Hb during weeks 28 to 36 within the target range of 10.0 to 12.0 g/dL without having received rescue therapy within 6 weeks prior to and during this 8-week evaluation period.

The average Hb value from weeks 28 to 36 weeks will be calculated as defined below. The Hb response will then be defined as a binary variable, Hb response (Yes/No), where Hb response="Yes" is defined as:

- Average Hb ≥ 10.0 g/dL, and
- Average Hb ≤ 12.0 g/dL.

For this calculation, all available Hb values in weeks 28-36 will be used, i.e. both scheduled and unscheduled Hb values from the central laboratory.

In case a subject does not have any available Hb value in weeks 28-36 (if they died or withdrew from the study for example), imputation rules will be used (refer to Section [7.11.1](#) for imputation rules).

In case a subject requires rescue therapy within 6 weeks prior to weeks 28-36, in weeks 22 to 36, values will be set to missing for 6 weeks after they stopped rescue and will be imputed similarly.

6.1.2.2 Change from BL in Low Density Lipoprotein (LDL) cholesterol to the average LDL cholesterol of weeks 12 to 28.

The analysis will be done on all values (fasted and non-fasted) of Day 1 and up to week 28.

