The model will contain treatment arm, region, CV History, previous ESA treatment, visits and visit by treatment as categorical variables. It will also contain baseline Hb and baseline Hb by visit as continuous variable.

The unstructured covariance pattern model will be used. If the algorithm for unstructured covariance pattern does not converge, then heterogeneous Toeplitz structure will be used. If this later model does not converge either, then the (homogeneous) Toeplitz structure will be tried. Finally, if none of them converge, first order autoregressive (AR (1)) as a covariance structure will be used to achieve convergence.

A similar model as the general example below will be used:

$$c_{ikjn} = \text{intercept} + \beta_n M_{\text{baseline},ikjn} + \tau_i + \alpha_n + (\alpha\tau)_{in} + \gamma_k + \varepsilon_{ikjn}$$

where

- c_{ikjn} is each analysis visit change from baseline of subject j in treatment arm i , and stratum k at time n ,
- β_n is the slope of c_{ikjn} at visit n as a function of the baseline Hb,
- $M_{\text{baseline},ikjn}$ is the baseline measurement of subject j in treatment arm i and stratum k at time n ,
- τ_i , is the mean effect of treatment arm i ,
- α_n is the mean effect at time n ,
- $(\alpha\tau)_{in}$ is the interaction term between treatment arm i and time n ,
- γ_k is the mean effect of stratum k ,
- ε_{ikjn} is the residual at time n for subject j in treatment arm i and stratum k .

The SAS procedure will be similar to the following:

```
proc mixed;
  class subject_id treatment previous_ESA_treatment region cv_history
    visit;
  model change = treatment previous_ESA_treatment region cv_history
    baseline_Hb visit treatment*visit;
  repeated visit /subject = subject id type=un;
  lsmeans visit*treatment / cl alpha = 0.05;
  estimate 'Roxadustat v.s. ESA averaged at weeks 28-36'
    treatment 1 -1
    treatment*visit 0 0 0 0 .. 0.2 0.2 0.2 0.2 0.2 -0.2 -0.2 -0.2
    -0.2 / cl;
  where visit in ('Week1', 'Week2', ..., 'Week8', 'Week10', ..., 'Week36');
run;
```

One analysis Hb value for each visit will be used, as defined in analysis windows in Section [7.11.4](#) and [Table 32](#)

Subjects receiving rescue therapy treatment within 6 weeks prior to and during this 8-week period will be set to missing and imputed similarly in the model (see Section [7.11.1](#) for imputation details).

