7.4.1.2 US (FDA) Primary Endpoint

7.4.1.2.1 Primary Analysis of the US (FDA) Primary Endpoint

The US (FDA) primary efficacy endpoint will be analyzed using the All Randomized.

The change from baseline to the average Hb of weeks 28 to 52 regardless of rescue therapy will be computed from an ANCOVA model with MI, adjusting for covariates defined in Section 7.4.1.1.1 comparing treatments (roxadustat vs. ESA).

The null hypothesis to be tested for the US primary efficacy analysis is:

- H_0 : Hb change from baseline in the roxadustat arm \leq Hb change from baseline in the ESA arm minus 0.75 g/dL

The alternative hypothesis H_1 is defined as the negation of the null hypothesis H_0 . The overall one-sided significance level (alpha) is fixed as 0.025. The study will be successful for the US primary endpoint if the null hypothesis is rejected.

ANCOVA model:

The following model will be used:

$$c_{ikj} = \text{intercept} + \beta M_{\text{baseline},ikj} + \tau_i + \gamma_k + \varepsilon_{ikj}$$

where

- c_{ikj} is the change from baseline to the average Hb values in weeks 28-52 of subject j in treatment arm i and stratum k ,
- β is the slope of c_{ikj} as a linear function of the baseline Hb,
- $M_{\text{baseline},ikj}$ is the baseline Hb of subject j in treatment arm i and stratum k ,
- τ_i is the mean effect of treatment arm i
- γ_k is the mean effect of stratum k
- ε_{ikj} is the residual for subject j in treatment arm i and stratum k .

The SAS procedure will be similar to the following:

```
proc mixed;  
  class treatment region CV_history previous_ESA_treatment;  
  model change = treatment previous_ESA_treatment region cv_history  
baseline_Hb;  
run;
```

ANCOVA with MI model:

The MI ANCOVA model will be used to compare the roxadustat and ESA groups in a fixed sequence procedure:

The following steps will be used to conduct the primary analysis.

1. Generate 1000 datasets, using seed 253056, where intermittent missing hemoglobin data will be imputed for each treatment relying on non-missing data from all subjects within each treatment group using the Monte Carlo Markov Chain (MCMC) imputation model with treatment, baseline hemoglobin, randomization stratification factors and the available non missing hemoglobin for each scheduled Week.
The MCMC statement in the SAS PROC MI procedure with monotone option will be used. As a result, each dataset will only have missing ending data, or a monotone missing data pattern.

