2. For each dataset from step 1, missing ending data (hemoglobin up through end of evaluation period) will be imputed using seed 35286853. As a result, 1000 imputed complete datasets will be generated.
 - Missing data at Week 1 will be imputed using the regression imputation model with baseline stratification factor, baseline and hemoglobin from Week 1, using the SAS PROC MI procedure with the REGRESSION option in the MONOTONE statement.
 - The SAS PROC MI procedure will use data separately from each treatment subjects to impute the missing data for a specific Week (i.e. only those that need the imputation for the Week). Since subjects from the different treatment groups for that Week are excluded from the step, they will not contribute to the imputation for the Week.

- Repeat for all other scheduled Weeks sequentially (Week 2 to the end of evaluation period). Subjects whose missing data were imputed for previous Weeks will contribute to the imputation for the current Week.

The regression imputation model includes an intercept and the slopes of the hemoglobin from previous Weeks and the stratification factors.

3. Analyze each imputed dataset using the ANCOVA using the mean of all observed or imputed Hb values within the evaluation period. The model will contain terms for baseline Hb measurement as a covariate and treatment arm and the other randomization stratification factors except screening Hb (≤ 11 vs > 11) as fixed effects.
4. Combine estimates from the results of each of the 1000 ANCOVA runs using SAS PROC MIANALYZE.

Report the results of the least-squares mean estimates of the change from baseline in hemoglobin during the evaluation period, the estimates of treatment effect (e.g., least-squares mean change from baseline in hemoglobin for the treatment group minus the least-squares mean change from baseline in hemoglobin for the ESA group) and the corresponding p-values and 95% CIs during the evaluation period. Summary statistics for the imputed data by MI will be presented too.

All available Hb values will be used for the calculation of the average in weeks 28 to 52, as defined in analysis windows in Section 7.11.4.

A forest plot will be generated showing subgroup factors on the y-axis and differences in mean changes from BL to the average in week 28-52 and their 95% confidence interval on the x-axis.

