Week 104/EOT (for completers)	Day 7 * (Week #) + 1	[Target Day – 98, Target Day + 28]	Week 104/EOT
EOT Visit (for premature discontinuations)	NA	NA	Analysis Visit corresponding to the actual visit window
Unscheduled	NA	NA	Analysis Visit corresponding to the actual visit window

^a: Relative to Day 1 (first dose date of study medication)

Analysis Visit windows, as depicted in [Table 34](#) below, will be used for the Lipid Panel, including LDL cholesterol efficacy study assessment:

Table 34 Analysis Visit Windows for Lipid Panel

CRF Visit	Target Day ^a	Analysis Visit Windows Actual Assessment Day	Analysis Visit
Day 1	Day 1	Day 1	Baseline
Week 4	Day 7 * (Week #) + 1	Day 2 to Day 42	Week 4
Week 8	Day 7 * (Week #) + 1	[Target Day – 14, Target Day + 13]	Week 8
Week 12	Day 7 * (Week #) + 1	[Target Day – 14, Target Day + 27]	Week 12
Week 20	Day 7 * (Week #) + 1	[Target Day – 28, Target Day + 27]	Week 20
Week 28	Day 7 * (Week #) + 1	[Target Day – 28, Target Day + 27]	Week 28
Week 36	Day 7 * (Week #) + 1	[Target Day – 28, Target Day + 27]	Week 36
Week 44	Day 7 * (Week #) + 1	[Target Day – 28, Target Day + 27]	Week 44
Week 52	Day 7 * (Week #) + 1	[Target Day – 28, Target Day + 55]	Week 52
Week 68	Day 7 * (Week #) + 1	[Target Day – 56, Target Day + 55]	Week 68
Week 84	Day 7 * (Week #) + 1	[Target Day – 56, Target Day + 69]	Week 84
Week 104/EOT (for completers)	Day 7 * (Week #) + 1	[Target Day – 70, Target Day + 28]	Week 104/EOT
EOT Visit (for premature discontinuations)	NA	NA	Analysis Visit corresponding to the actual visit window
EOS Visit	NA	Last assessment between Day 2 and study termination day	EOS
Unscheduled	NA	NA	Analysis Visit corresponding to the actual visit window

^a: Relative to Day 1 (first dose date of study medication)

For the MMRM analyses, which require one value per visit, one analysis value for each visit will be used.

For the ANCOVA analyses, which use the average, all available values in the analysis windows will be used for the calculation.

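### The Hb-response average in key secondary Test 1 weights every sample equally, so responder status depends on how often a subject is re-tested

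*SAP*

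**What the plan says.** SAP 6.1.2.1 classes a subject as a responder if the week 28 to 36 average lies between 10.0 and 12.0 g/dL. On the values that enter it: "For this calculation, all available Hb values in weeks 28-36 will be used, i.e. both scheduled and unscheduled Hb values from the central laboratory".

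SAP 7.11.4 sets two rules side by side. For the repeated-measures models: "For the MMRM analyses, which require one value per visit, one analysis value for each visit will be used". For ANCOVA: "For the ANCOVA analyses, which use the average, all available values in the analysis windows will be used for the calculation". The US primary analysis (SAP 7.4.1.2.1) is an ANCOVA with multiple imputation, and there: "All available Hb values will be used for the calculation of the average in weeks 28 to 52". Its imputation steps, however, work by scheduled week.

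Re-tests reach these data through footnote i to the protocol's Schedule of Assessments: "If during an unscheduled visit hemoglobin needs to be assessed, this should always be done with the HemoCue AND a central laboratory hemoglobin assessment".

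Table 17 puts Hb response first in the fixed sequence, with a margin of -15%. The sensitivity analyses in Table 18 change the analysis set (S1) or the handling of rescue (S2). Neither changes how the average is formed.

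**The concern.** The plain reading of an average over all values is an unweighted mean, so a visit window with several samples counts several times. Unscheduled Hb checks are likely to cluster where Hb is low or high, and the subject average is then pulled toward the out-of-range values. A subject whose visits average within 10.0 to 12.0 g/dL can be classed as a non-responder because of re-testing alone.

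This matters most for Test 1, because a failure there stops every later key secondary test. Treatment is open label. The roxadustat arm has its own Hb-triggered dosing rules (Protocol 5.1.2.1, Table 4), while the ESA arm follows the SmPCs, so re-testing could differ by arm. The same averaging applies, on the plain reading, to the ANCOVA analyses: the US primary and its ANCOVA sensitivity analyses, and EU sensitivity analysis S5. The mean monthly IV iron ANCOVA is not affected, because it uses total milligrams over time.

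**Working it through.** **The plan's own figures.** The point disputes no sample size, but the stated power reproduces. US: SE = 1.5 × √(2/375) = 0.1095; (0.75 - 0.25)/0.1095 = 4.56; Φ(4.56 - 1.96) = 99.5%, against at least 99% stated. This borrows the EU difference and SD, because SAP section 4 gives none for the US endpoint. EU, with 300 per arm and one-sided alpha 0.0174: 97.6%, against 97% stated.

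**One subject (illustrative values).** Scheduled values at weeks 28 to 36: 10.6, 10.4, 9.4, 10.2, 10.5. Unscheduled values near week 32: 9.0, 8.9, 9.3.
- All values: 78.3/8 = 9.79, non-responder. The week 32 window carries 4/8 = 50% of the weight.
- Window first: the week 32 mean is (9.4 + 9.0 + 8.9 + 9.3)/4 = 9.15. The average is (10.6 + 10.4 + 9.15 + 10.2 + 10.5)/5 = 50.85/5 = 10.17, responder. Each window carries 20%.
- Scheduled values only: 51.1/5 = 10.22, responder.

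Four samples in one 14-day window is an extreme case. It shows the mechanism, not a typical size.

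**Simulation.** The documents give no re-test rate, so every input on re-testing is an assumption. True Hb is identical in the two arms and only one arm is re-tested.

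Model A: five visits, mean Hb 10.9 g/dL, between- and within-subject SD 0.7 each, visit-to-visit AR(1) correlation 0.6, re-test noise SD 0.25, and a re-test every time the trigger is met.

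| Trigger (g/dL) | Extra samples | Response, window first | Response, all values | Change (points) |
|---|---|---|---|---|
| <9.0 or ≥13.0 (action thresholds in Protocol 5.1.2.1) | 1 | 75.1% | 74.4% | -0.7 |
| same | 2 | 75.1% | 74.2% | -0.9 |
| <9.5 or >12.5 (assumed) | 1 | 75.0% | 71.1% | -3.9 |
| same | 2 | 75.0% | 68.8% | -6.2 |
| <9.5 only (assumed) | 1 | 75.0% | 72.9% | -2.1 |
| same | 2 | 75.0% | 71.5% | -3.5 |

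At the protocol thresholds with only half of the triggers re-tested, the change is 0.3 to 0.5 points.

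Model B: mean 11.0 or 11.4, the same SDs, two re-tests per trigger, several triggers, and 25% to 100% re-testing.
- The responder difference ran from about -0.2 to -6 points. Full one-arm re-testing at ≥13 or <9 gave -2.8, so the figure of under 1 point depends on the variance structure assumed in Model A.
- Averaging within the visit first left 1.6 points or less.
- Equal 50% re-testing in both arms gave no arm difference, although 0.6% to 3% of subjects still changed responder status.

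**Mean Hb.** Low-only re-testing in Model A moved the mean by 0.025 to 0.041 g/dL, and the extreme in Model B was about 0.07. Against the 0.75 margin these are 0.041/0.75 = 5% and 0.07/0.75 = 9%. Even with 0.07 against roxadustat, US power is Φ(0.43/0.1095 - 1.96) = Φ(1.97) = 97.6%.

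**Direction.** Re-testing out-of-range values lowers the response rate of the arm that is re-tested. Extra re-testing under roxadustat is therefore conservative for non-inferiority. Extra re-testing under ESA favours roxadustat.

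**The case against.** The strongest case against is that no bias has been shown. The documents contain no re-test rate and no arm difference, equal re-testing largely cancels, and the 4 to 6 points come from triggers that the protocol does not use. Visits in weeks 28 to 36 are already two-weekly, which limits the need for extra checks. For Test 1, values after rescue are set to missing for 6 weeks, which removes part of any low cluster. All of this stands, and it limits the size. It does not answer the point that responder status depends on sample count and that no planned analysis tests this.

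Three stronger readings are tempting and not supported:
- A reader might infer that the US primary result is at risk. The shift is small against 0.75 g/dL, and sensitivity analyses S3 and S4 in Table 15 are repeated-measures models with one value per visit. Nor is it settled that the US average is weighted by sample count: the imputation runs by scheduled week, and the SAP does not say how unscheduled values join it.
- A reader might infer that the two rules in SAP 7.11.4 contradict each other, or that the MMRM is free of the problem. The rules are openly prespecified for different models. The MMRM gives each visit equal weight but keeps the latest value in a window, so an unscheduled value can replace the scheduled one.
- A reader might infer that the week 28 to 52 average is wrong because 5 of 9 scheduled values (56%) fall in weeks 28 to 36, whose windows cover 77 of 189 days (41%). The schedule is the same in both arms and no arm bias follows. Weighting by window length is a preference, not a correction.

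**Conclusion.** The point holds for Test 1 and, on the plain reading of SAP 7.11.4, for the ANCOVA averages: the subject average depends on how often Hb was sampled, and for Test 1 no sensitivity analysis covers it. An arm bias needs re-testing that differs by arm, and that remains a possibility, not a finding.

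Under Model A with one arm alone re-tested, the spurious responder difference is under 1 point at the protocol's thresholds and about 4 to 6 points at the assumed wider ones, against 15. Model B's 2.8 points for ≥13 or <9 shows how far the lower figure depends on its assumptions. The effect on the US primary mean is negligible, and the EU primary MMRM does not use this average. This is a worthwhile tightening of Test 1, not a threat to either primary endpoint.

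**What to change.** In SAP 6.1.2.1 and 7.11.4, state that all eligible central-laboratory values are first averaged within each Table 32 analysis window, and that the subject average is the equal-weight mean of the window means over the evaluation period. Apply the same rule to the ANCOVA averages, so that one value per scheduled week enters the imputation in SAP 7.4.1.2.1; this also settles how unscheduled values are combined with imputed weeks. Do not add window-length weighting for weeks 28 to 52.

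Keep the all-values mean as a sensitivity analysis, added to Table 18 for Hb response, and report the number of unscheduled Hb values by arm so that any difference in re-testing can be seen.

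The cost is a short SAP edit, a small derivation change and a small departure from the existing all-values rule. No data are discarded, because unscheduled values still count within their window.

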7.11.5 End of Safety Emergent Period

The end of Safety Emergent Period will be defined as:

- minimum between [(Analysis Date of last dose + 28 days + x), EOS visit, Date of death], with x corresponding to additional days based on the last dosing frequency.

The value of x days is defined to standardize to 3 times per week,:

if frequency = “3 TIMES PER WEEK” then x=0

if frequency = “2 TIMES PER WEEK” then x=1

if frequency = “1 TIME PER WEEK” then x=5

if frequency = “EVERY 2 WEEKS” then x=12

if frequency = “QM” then x =26 days.

With Analysis Date of Last Dose defined in Section [6.5.4](#)

